2.4.1 Fluorescence In-situ Hybridization (FISH) for *TAZ-CAMTA1* gene fusion

We believe EHE most likely to respond to MEK inhibition are tumors that harbor the *TAZ-CAMTA1* translocation because MEK activation requires TAZ-CAMTA1 expression (see section 2.4.2). In pathology review of tumors that morphologically resembled EHE, over 90% of the tumors contained *TAZ-CAMTA1* gene fusion detected by FISH (Tanas et

al. 2011). Therefore, we believe most, if not all, patients enrolled in this trial will have tumor that contains *TAZ-CAMTA1* gene fusion. A fusion FISH test has been developed at Cleveland Clinic and will be used to evaluate the presence of the *TAZ-CAMTA1* gene fusion in tumor from patients enrolled in the trial. Archival formalin-fixed, paraffin-embedded tumor samples will be collected and processed by the SARC SPORE pathology core. Representative H&E stained sections will be reviewed by the pathology core as a central review of the diagnosis. Fusion FISH for *TAZ-CAMTA1* will be performed on unstained sections from diagnostic tissue using the CLIA-certified FISH laboratory at Cleveland Clinic after enrollment (See section 9.1). Tumors with at least 10% fused gene signals will be considered positive for *TAZ-CAMTA1* gene fusion and will be scored as *TAZ-CAMTA1* fusion detected. Tumors with less than 10% fused gene signals will be scores as *TAZ-CAMTA1* fusion not detected. Tumor in which the fusion FISH test is not informative for technical reasons including lack of sufficient tumor tissue in the sample/slide will be scored as test failed.

[figure not shown]

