2.4.3 Biomarkers of EHE activity in patients treated with trametinib

Plasma CTGF levels may be a useful biomarker of EHE survival as CTGF is a secreted protein whose gene is an immediate downstream target of TAZ-CAMTA1 (Tanas et al., 2016). CTGF is secreted and binds to α IIb β 3 integrin on the cell surface, leading in an autocrine fashion to downstream activation of RAS and MAP kinase pathways. This signal transduction pathway drives TAZ-CAMTA1-mediated NIH/3T3 cell transformation. Inhibition of any portion of this pathway inhibits transformation. This pathway is summarized in Figure 2. Preliminary studies have shown that CTGF is produced at high levels and secreted into culture media by cells that express TAZ-CAMTA1.

CTGF is secreted by EHE and can be quantified in plasma from EHE patients using enzyme-link immunosorbent assay (ELISA). If trametinib results in EHE cell death and objective tumor response, we hypothesize that CTGF plasma levels will decline. Alternatively, if trametinib blocks growth of EHE by inhibiting MEK but does not result

in cell death, we expect CTGF plasma levels will remain unchanged because the production and secretion of CTGF is upstream of the RAS and MAP kinase pathways. Additionally, patients with advanced EHE have elevated c-reactive protein levels and erythrocyte sedimentation rate in the blood (unpublished observation) which may be related to tumor production of CTGF. Blood from patients will be obtained prior to starting trametinib, approximately 4 weeks and 6 months after start of treatment with trametinib, and at the time objective tumor response or progression is identified to explore the relationship between trametinib treatment, plasma levels of circulating CTGF, c-reactive protein levels and erythrocyte sedimentation rate. ELISA for CTGF quantification will be performed by a central reference laboratory and CRP and ESR will be determined by local CLIA-certified laboratories using standard methods.

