13. STATISTICAL CONSIDERATIONS

13.1 Study Design/Endpoints

The primary endpoint is the objective response rate using RECIST 1.1. Tumor response assessed by the local site investigator or delegate will be used to assess the objective response rate. Tumor response will be centrally reviewed by [name] but the local site assessment will be used to determine patient treatment and tumor response outcome.

A Simon minimax sampling two-stage design will be used to estimate the objective response rate with a goal of at least 20% of patients to be considered as having preliminary evidence of activity and less than 5% indicating that trametinib is ineffective as a potential EHE treatment. Thirteen patients with EHE will be enrolled in stage I, and if there is at least one objective response as defined by RECIST 1.1, additional patients with EHE will be enrolled until 27 patients with EHE in which *TAZ-CAMTA1* translocation is detected by fusion FISH in archival tumor tissue have been registered and started treatment. The diagnosis of EHE will be determined by the local site, but the presence of *TAZ-CAMTA1* translocation will be determined by the Cleveland Clinic FISH laboratory. If four or more objective tumor responses are documented among 27 patients with *TAZ-CAMTA1* translocation positive EHE, trametinib will be considered to have activity in EHE. With a type 1 error of 5%, this design will have a power of approximately 80% and will have a 51% probability of terminating after the first step if the response rate is 5%. The ORR, 6-month PFS and 2-year OS rates will be calculated along with their 95% confidence intervals. PFS and OS will be estimated by the Kaplan-Meier method.

In stage I enrollment, the presence of *TAZ-CAMTA1* translocation was not detected in 3 tumor samples and in one case there was insufficient tumor tissue available for the analysis. The rate of *TAZ-CAMTA1* translocation negative EHE is higher than the expected rate of less than 10%, and because we anticipate activation of the MAP kinase pathway to occur in tumor with expression of *TAZ-CAMTA1* but not in tumor without the translocation, the protocol is amended to enroll at least 27 patients with EHE containing *TAZ-CAMTA1* translocation.

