Evaluation of MAP kinase activation is an exploratory analysis on relatively few samples. In another multicenter SARC phase II clinical trial (SARC028) that required paired pre-treatment and on-treatment tumor biopsy, matched samples were obtained in 75% of the cases and tumor biopsy was performed in about 50% of patients at the time of progression. We estimate a similar success rate in obtaining matched tumor tissue. Descriptive statistics will be generated, and estimates for the proportion of samples with demonstrated inhibition of MAPK signaling post-treatment compared to pre-treatment will be generated along with 95% confidence intervals. Likewise, the proportion of patients with demonstrated MAPK signaling inhibition at time of disease progression will be determined with the corresponding 95% confidence interval. These are exploratory analyses and all available data will be used.

Evaluation of presence of *TAZ-CAMTA1* gene fusion will be performed by FISH. Tumor in which at least 10% of nuclei are scored as having a fused signal will be counted as EHE with presence of *TAZ-CAMTA1* translocation. The number and percent of *TAZ-CAMTA1* gene fusion positive EHE will be reported.

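### Section 13.4 pools all biopsy samples for the MAPK-inhibition proportion without a split by TAZ-CAMTA1 status, so it may understate inhibition in fusion-positive tumours (minor)

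*Combined protocol and SAP*

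**What the plan says.** Section 13.4 describes the MAPK work modestly: "Evaluation of MAP kinase activation is an exploratory analysis on relatively few samples". It then plans the main summary: "estimates for the proportion of samples with demonstrated inhibition of MAPK signaling post-treatment compared to pre-treatment will be generated along with 95% confidence intervals". A second proportion, inhibition at progression, is handled the same way, and the paragraph closes with "These are exploratory analyses and all available data will be used". Neither 13.4 nor Section 9.3.2, which describes the phospho-ERK assays, separates samples by fusion status or says how to count a pair that shows no phospho-ERK before treatment.

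Section 13.1 explains the amendment. In stage I the translocation "was not detected in 3 tumor samples and in one case there was insufficient tumor tissue", against an expected fusion-negative rate below 10%. Enrolment was therefore extended to reach 27 fusion-positive patients, "because we anticipate activation of the MAP kinase pathway to occur in tumor with expression of *TAZ-CAMTA1* but not in tumor without the translocation". Section 2.4.1 states the same belief: "MEK activation requires TAZ-CAMTA1 expression".

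Section 13.1 also assigns populations. Responses for the activity decision are counted among 27 fusion-positive patients. Six-month PFS, median PFS and 2-year OS are analysed in fusion-positive patients, and safety and PROMIS in all treated patients. It assigns no population to the MAPK analysis. Section 9.3.2.1 makes the biopsies optional.

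**The concern.** On the protocol's own premise, a fusion-negative tumour has no MAPK activation for trametinib to switch off. If a pair from such a tumour stays in the denominator and is scored as not inhibited, it lowers the reported proportion whatever the drug does.

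Phospho-ERK is the trial's most direct evidence on whether trametinib reaches its target in EHE. Plasma CTGF cannot stand in for it, because Section 2.4.3 expects CTGF to stay unchanged if MEK is blocked without cell death. If the response rate is low, the phospho-ERK proportion helps to tell a drug that missed its target from one that hit it without benefit. A pooled proportion blurs that reading, and it cannot be set directly beside PFS and OS, which describe fusion-positive patients.

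**Working it through.** **Plan's own figures.** The plan states no expected value for the MAPK proportion, so there is none to reproduce. Its two-stage response design (13 then 27 patients, continue with at least 1 response, success with at least 4) does reproduce: type I error 4.2%, power 80.1% and early-stop probability 51.3%, against the stated 5%, about 80% and 51%. Nothing below changes those figures.

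**Inputs from the documents**
- Expected fusion-negative rate at design: below 10% (13.1).
- Stage I: 13 patients planned, 3 not detected, 1 with insufficient tissue (13.1). Informative samples: 13 − 1 = 12. Share negative: 3/12 = 25% (exact 95% CI 6–57%, so loosely known).
- Matched-pair rate: 75%, borrowed from another sarcoma trial in which paired biopsy was required (13.4).

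**Assumptions**
- True inhibition in fusion-positive pairs is 80%. The documents give no value.
- The biopsied patients have the same fusion mix as the enrolled patients.

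**Formula.** With f the share of analysed pairs that are fusion-negative, and p₊ and p₋ the proportions scored as inhibited in each group:

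pooled proportion = p₊(1 − f) + p₋f

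| f | p₋ = 0 | p₋ = 40% (half) | p₋ = 80% (equal) |
|---|---|---|---|
| 0 | 80% | 80% | 80% |
| 10% | 0.8 × 0.90 = 72% | 72% + 4% = 76% | 80% |
| 25% | 0.8 × 0.75 = 60% | 60% + 10% = 70% | 80% |

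**In counts, with p₋ = 0 and exact (Clopper-Pearson) intervals.** Section 13.2 opens a further slot for each unconfirmed case until 27 fusion-positive patients have started treatment. At 75% pairing these give 0.75 × 27 ≈ 20 pairs, of which 16 are taken as inhibited.
- Fusion-positive pairs only: 16/20 = 80% (56–94%).
- f = 10%: 27/0.90 = 30 treated, 3 of them negative, about 2 negative pairs. Pooled 16/22 = 73% (50–89%).
- f = 25%: 27/0.75 = 36 treated, 9 of them negative, about 7 negative pairs. Pooled 16/27 = 59% (39–78%).

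Because biopsies are optional here, 20 pairs is probably an upper estimate. With 10 fusion-positive and 2 fusion-negative pairs, 8/10 = 80% (44–97%) becomes 8/12 = 67% (35–90%).

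**The case against.** The strongest reply is that understatement needs three things the documents do not establish.
- Fusion-negative patients must supply matched pairs. Biopsies are optional, and nothing says that any such patient was biopsied.
- Their tumours must lack active ERK. Sections 13.1 and 2.4.1 offer this as an expectation and a belief, not a result.
- A pair without baseline signal must be scored as not inhibited. Section 13.4 has no such rule, and inhibition relative to baseline is arguably undefined there, so such pairs might simply be left out.

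The reply adds that using all data is a stated choice for an openly exploratory analysis with no test, error rate or decision attached. Fusion-negative pairs are also the trial's only in-patient evidence on whether activation really depends on the fusion. The pooled and fusion-positive intervals overlap heavily. The progression proportion is little exposed, because 9.3.2.1 limits progression biopsies to patients who had responded.

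All of this stands, and it makes the effect conditional and the priority low. It does not remove the gap. The missing counting rule is itself part of the problem, and the value of fusion-negative pairs argues for showing them separately, since pooling hides that comparison.

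**Conclusion.** The point holds in conditional form and is minor. As written, 13.4 can mix into one proportion pairs that 13.1 expects to have nothing to inhibit. Under the stated assumptions, a true 80% would read as 72% at 10% negative and 60% at 25%. The loss is smaller if fusion-negative tumours show some inhibition. It is zero if they show as much as fusion-positive ones, or if they supply no pairs.

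A reader might infer more than the documents support:
- *That the proportion will be too low by a definite amount.* The 80% is assumed, and both the share of negative pairs and their scoring are unknown.
- *That the negative share is 4/13 = 31%.* This counts the tumour with insufficient tissue as negative, when its status is unknown.
- *That response results come from fusion-positive patients only.* This matches the decision rule in 13.1, but 13.5.2 puts every eligible patient with at least one dose into the main response analysis. That conflict is a separate issue. The mismatch with PFS and OS does not depend on it.
- *That the CTGF analysis has the same fault.* Section 13.4 enters CTGF, with CRP and ESR, as time-dependent variables in a Cox model. There is no proportion to dilute, and the sentence about using all data sits in the MAPK paragraph.

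**What to change.** In 13.4, keep all pairs but report the phospho-ERK inhibition proportion, with its 95% confidence interval, by FISH result: detected, not detected, and failed or not performed. Make the detected row the main result and show the others descriptively.

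State in advance how a pair without baseline phospho-ERK is counted: scored as not inhibited, or left out of the denominator with the number given. This rule is needed in every row, since a fusion-positive pair can also lack baseline signal. Settling it before the phospho-ERK results are read avoids a choice of denominator after the fact.

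The cost is wording only. FISH is already planned for enrolled patients with available tissue, and no data are discarded. The main row rests on fewer pairs, so its interval may be slightly wider, most clearly if inhibition is equal in both groups. In the 25% illustration the widths are about the same: 94 − 56 = 38 points for fusion-positive pairs and 78 − 39 = 39 points pooled.

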13.5 For phase 2 protocols only: Reporting and Exclusions

13.5.1 Evaluation of Toxicity

All patients will be evaluable for toxicity from the time of their first treatment with Trametinib.

13.5.2 Evaluation of Response

All patients included in the study must be assessed for response to treatment, even if there are major protocol treatment deviations or if they are ineligible. Each patient will be

assigned one of the following categories: 1) complete response, 2) partial response, 3) stable disease, 4) progressive disease, 5) early death from malignant disease, 6) early death from toxicity, 7) early death because of other cause, or 9) unknown (not assessable, insufficient data).

All of the patients who met the eligibility criteria and took at least 1 dose of trametinib will be included in the main analysis of the response rate. Patients in response categories 4-9 will be considered to have a treatment failure (disease progression). Thus, an incorrect treatment schedule or drug administration does not result in exclusion from the analysis of the response rate.

REFERENCES

Agulnik, M., JL Yarker, SH Okuno, *et al.* (2013). An open-label, multicenter, phase II study of bevacizumab for the treatment of angiosarcoma and epithelioid hemangioendotheliomas. *Ann Oncol.* 24:257-2563

Balagula, Y., K. Barth Huston, K.J. Busam, *et al.* (2010). Dermatologic side effects associated with the MEK 1/2 inhibitor selumetinib (AZD6244, ARRY-142886). *Invest New Drugs.* 29:1114-1121.

Bekaii-Saab, T., M.A. Phelps, X. Li, *et al.* (2011). Multi-institutional phase II study of selumetinib in patients with metastatic biliary cancers. *J Clin Oncol.* 29:2357-2363.

Bendell, J., P. LoRusso, E. Kwak, *et al.* (2011). Clinical combination of the MEK inhibitor GDC-0973 and the PI3K inhibitor GDC-0941: A first-in-human phase Ib study in patients with advanced solid tumors. *AACR Meeting Abstracts.* Abstract LB-89.

Blumenschein, G.R., E.F. Smit, D. Planchard, *et al.* (2013). MEK114653: A randomized, multicenter, phase II study to assess efficacy and safety of trametinib (T) compared with docetaxel (D) in KRAS-mutant advanced non-small cell lung cancer (NSCLC). *J Clin Oncol.* 31:Abstract 8029.

Borthakur, G., J.M. Foran, T. Kadia, *et al.* (2010). GSK1120212, a MEK1/MEK2 inhibitor, demonstrates acceptable tolerability and preliminary activity in a dose rising trial in subjects with AML and other hematologic malignancies. *Blood (ASH Annual Meeting Abstracts).* 116:Abstract 3281.

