Secondary objectives of the 6-month PFS rate, median PFS, and 2-year OS rate will be determined from analyses of patients with *TAZ-CAMTA1* translocation positive EHE. Evaluation of the safety of trametinib, and patient reported symptoms using NIH-PROMIS questionnaires will be determined from analyses of all patients who started treatment with trametinib.

Progression-free survival will be calculated from time of first dose of study medication to occurrence of radiologic tumor progression per RECIST1.1, clinical progression based on treating physician's assessment or death from any cause. Overall survival will be calculated from the time of first dose of study drug to occurrence of death from any cause. Patients who are registered and are determined to be eligible for study treatment but do not start study drug will be replaced. All patients who receive study drug for any period of time will be evaluable for toxicity. The rates of adverse events occurring in at least 5% of subjects and rates of grade 3-5 adverse events will be tabulated by system and term using Common Terminology Criteria of Adverse Events (CTCAE). For dose adjustment schedule see Section 6.1. PROMIS questionnaires will be scored according to recommended standardized system and t-scores generated. A mixed model will be used to analyze change in t-scores over time. Whether or not having evidence of disease progression will be used as a time-dependent variable in the mixed model with adjustment of other potential confounding variables.

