13.2 Sample Size/Accrual Rate

This study will be conducted in a two-stage process. In stage I, 13 patients with EHE will be enrolled. If there is at least 1 objective response, additional patients will be enrolled in stage II until there is evidence that a total of 27 patients with EHE with *TAZ-CAMTA1* translocation detected by fusion FISH have been registered and started treatment. After 27 patients have been enrolled and started treatment, enrollment of additional patients will be held until FISH testing is performed on available tissue from the enrolled patients. One enrollment slot will be opened for each case of FISH result of *TAZ-CAMTA1* translocation "not detected", "test failed", or "test not performed" (no tumor tissue in sample) until a total of 27 patients have enrolled and started treatment with FISH result of *TAZ-CAMTA1* translocation "detected". Enrollment in the second stage will be held until at least 1 objective response has occurred. Enrollment for stage I is anticipated to be complete within the first 12 months of study activation. Enrollment for stage II is anticipated to be complete within 18 months of proceeding to stage II. We anticipate that on average, 1 patient per month will be accrued to the study. The study is open to all eligible persons at least 15 years of age. Because of the very rare nature of the disease under study, we will not restrict enrollment based on sex, race or ethnicity in order to complete accrual within 2-3 years.

PLANNED ENROLLMENT REPORT

Racial Categories	Ethnic Categories				Total
	Not Hispanic or Latino		Hispanic or Latino		
	Female	Male	Female	Male	
American Indian/ Alaska Native	0	0	0	0	0
Asian	1	1	0	0	2
Native Hawaiian or Other Pacific Islander	0	0	0	0	0
Black or African American	3	2	0	0	5
White	9	6	2	1	18
More Than One Race	1	1	0	0	2
Total	14	10	2	1	27

PHS 398 / PHS 2590 (Rev. 08/12 Approved Through 8/31/2015)

OMB No. 0925-0001/0002

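### The main response-rate set in 13.5.2 is not the 27-patient set that the 13.1 success rule uses, and no passage says which one carries the primary ORR and its 95% CI

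*Combined protocol and SAP*

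**What the plan says.** The primary objective (1.1) is to estimate the ORR by RECIST 1.1.

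- **Success rule (13.1).** "If four or more objective tumor responses are documented among 27 patients with" the translocation, trametinib is considered active.
- **Estimate (13.1).** "The ORR, 6-month PFS and 2-year OS rates will be calculated along with their 95% confidence intervals". This sentence names no analysis set.
- **Other endpoints (13.1).** "Secondary objectives of the 6-month PFS rate, median PFS, and 2-year OS rate will be determined from analyses of patients with" translocation-positive EHE. Safety and PROMIS "will be determined from analyses of all patients who started treatment with trametinib". ORR appears in neither assignment.
- **Main response-rate analysis (13.5.2).** "All of the patients who met the eligibility criteria and took at least 1 dose of trametinib will be included in the main analysis". Response categories 4 to 9 count as failures.
- **Replacement (13.2).** "One enrollment slot will be opened for each case of FISH result of" not detected, failed or not performed, "until a total of 27 patients have enrolled and started treatment with FISH result of" detected.
- **Stage I experience (13.1).** The translocation "was not detected in 3 tumor samples and in one case there was insufficient tumor tissue available for the analysis".
- **Eligibility (3.1.2).** Tissue must be available for FISH, but a positive result is not required. FISH is done after enrollment (2.4.1).

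**The concern.** Two current sections describe the response analysis in different patients. A fusion-negative patient can be eligible and treated, so 13.5.2 includes that patient and the 13.1 rule does not. Because 13.1 assigns a population to PFS, OS, safety and PROMIS but not to ORR, the only text that defines a main response-rate analysis is 13.5.2. Followed literally, it yields a primary ORR and CI from a set that the success rule does not test.

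The primary objective is estimation, so the denominator is part of the primary result. It should be fixed before responses are known. That matters more here because the trial is open-label, response is assessed by the local site (13.1), and the principal investigator and statistician can see the data at all times (12.1).

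**Working it through.** **1. The plan's own design figures.** Inputs from 13.1: p0 = 5%, p1 = 20%, n1 = 13 (continue with at least 1 response), N = 27 (success with at least 4).

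P(success | p) = sum over x = 1 to 13 of P(X1 = x) × P(X2 ≥ max(0, 4 − x)), with X1 ~ Bin(13, p) and X2 ~ Bin(14, p).

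- p = 0.05: type 1 error 0.0416; early stop 0.95^13 = 0.513.
- p = 0.20: power 0.801.

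These agree with the stated 5% limit, about 80% and 51%. Section 13.5.2 contains no threshold, so it changes none of them.

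**2. Size of the 13.5.2 set.** Stage I: 13 − 3 not detected − 1 insufficient tissue = 9 positive. Positives still needed: 27 − 9 = 18. Assume that the stage I patients were treated and met the other criteria.

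| Scenario | N in 13.5.2 set |
|---|---|
| All later patients positive; insufficient-tissue patient ineligible | 12 + 18 = 30 |
| All later patients positive; that patient eligible | 13 + 18 = 31 |
| 90% positive in stage II | 13 + 18/0.90 = 33 |
| Stage I rate among tested, 9/12 | 13 + 18/0.75 = 37 |
| Stage I rate among enrolled, 9/13 | 13 + 18/(9/13) = 39 |

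The 90% figure reflects the expected negative rate of less than 10%, which 13.1 says stage I exceeded.

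**3. Effect on the estimate.** Exact (Clopper-Pearson) 95% CI, all responders fusion-positive:

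| Denominator | 4 responses | 6 responses |
|---|---|---|
| 27 | 14.8% (4.2 to 33.7) | 22.2% (8.6 to 42.3) |
| 30 | 13.3% (3.8 to 30.7) | 20.0% (7.7 to 38.6) |
| 31 | 12.9% (3.6 to 29.8) | 19.4% (7.5 to 37.5) |
| 33 | 12.1% (3.4 to 28.2) | 18.2% (7.0 to 35.5) |
| 39 | 10.3% (2.9 to 24.2) | 15.4% (5.9 to 30.5) |

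Six responses exceed the 20% goal on 27, equal it on 30 and fall below it on 31 or more.

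**4. Direction.** Suppose four fusion-positive patients and one other patient respond. Then 4/27 = 14.8% compares with 5/31 = 16.1% (5.5 to 33.7), and the larger set gives the higher rate.

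**5. Mismatch the other way.** Section 13.2 counts patients who enrolled, started treatment and are FISH-positive, with no eligibility condition, while 13.5.2 requires eligibility. One positive patient later found ineligible would stay in the 27 but leave the 13.5.2 set. In the N = 30 scenario that set would then be 26 + 3 = 29.

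**The case against.** The best defence is that 13.1 governs. It is the specific rule, amended because MAP kinase activation is expected only with the fusion. Section 13.5.2 sits under a generic phase 2 heading and closes by barring exclusions for dosing errors, so its purpose may be only to prevent post hoc exclusions. One can also argue that a decision in fusion-positive patients beside an estimate in all treated patients is coherent, since 1.1 does not restrict the ORR by fusion status. Finally, the shifts in the estimate are small beside intervals roughly 21 to 34 points wide.

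Much of this stands. The intent of 13.1 is clear for the decision, and either population could be defended for the estimate. What does not follow is that the text has chosen one. Section 13.5.2 calls its analysis the main one, and the paragraph in 13.1 that assigns populations omits ORR.

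A reader might also infer that the false-positive rate is inflated. Applying four or more responses to the 13.5.2 set would give a type 1 error of 0.056 at N = 30 and 0.062 at N = 31. No passage applies the rule to that set, so the documents do not support this.

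**Conclusion.** The inconsistency is real and worth fixing, but it is limited to the reported primary ORR and its CI. The 13.1 decision rule and its error rates are untouched.

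At least three patients are in the 13.5.2 set but not in the 27, provided the three not-detected stage I patients were eligible and dosed; the documents imply this but do not say so patient by patient. A fourth counts if the insufficient-tissue patient is judged eligible under 3.1.2. It would be tempting to say that the 13.5.2 set must be larger by at least three. That does not follow, because a fusion-positive patient found ineligible would reduce it.

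Nor is there a fixed bound or direction for the shift. With all responders fusion-positive, it runs from 14.8 − 13.3 = 1.5 points (4 responses, N = 30) to 22.2 − 15.4 = 6.8 points (6 responses, N = 39) across the scenarios shown. It can reverse if a patient outside the 27 responds.

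**What to change.** In 13.5.2, with a cross-reference in 13.1, state that the primary ORR and its 95% CI use the same patients as the rule of four or more: the 27 who were registered, started treatment and have a FISH result of detected. Use the 13.2 definition as it stands, with no further exclusion for ineligibility found later. Keep the existing rule that categories 4 to 9 are failures. Report the ORR with 95% CI in all eligible treated patients as a supportive estimate with no decision rule.

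The cost is one or two sentences, a cross-reference and one extra supportive estimate. No new patients, data or assessments are needed.
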